## 2.2 Violations and deviations

The list of all IPDs is provided in the AstraZeneca NHP. The IPD are classified per the AstraZeneca NHP. Refer to this document for all details about protocol deviations. Relevant IPDs used to exclude subject from the sensitivity analysis 1 are reported below:

- All IPDs included in the category 1 - Inclusion Criteria Deviations (Subject who did not meet the below criteria. Those who entered the study even though they did not satisfy the entry criteria. If Screen failure, then this is not PD);
- All IPDs included in the category 2 - Exclusion Criteria Deviations (Enrolled, even though subject fulfilled the below criteria. Those who entered the study even though they did not satisfy the entry criteria. If Screen failure, then this is not PD);
- All IPDs included in the category 3 - Discontinuation Criteria for study product met but patient not withdrawn from study treatment.
- All IPDs included in the category 5 - Investigational Product (IP) Deviation, with the except of the IPD 5.02 - Subjects who were randomised but did not receive IP which is not considered relevant.
- All IPDs included in the category 6 - Excluded Medications taken.

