## 6.3 Measures to Minimise Bias: Randomization and Blinding

All participants will be centrally assigned to randomized study intervention using a RTSM

system. Before the study is initiated, the telephone number and call-in directions and/or the log in information & directions for the RTSM will be provided to each site.

To simplify supply of study drug, randomization will be stratified based on the region in which the site is located. This will achieve greater balance within each region compared to simple randomization. Currently, two regions are planned: Europe and North America.

Study intervention will be dispensed at the study visits summarized in SoA.

The RTSM will provide to the Investigator(s) or pharmacists the kit identification number to be allocated to the participant at the dispensing visit. Routines for this will be described in the RTSM user manual that will be provided to each centre.

The randomisation code should not be broken except in medical emergencies when the appropriate management of the participant requires knowledge of the treatment randomisation. The Investigator documents and reports the action to AstraZeneca, without revealing the treatment given to participant to the AstraZeneca staff. AstraZeneca retains the right to break the code for SAEs that are unexpected and are suspected to be causally related to an investigational product and that potentially require expedited reporting to regulatory authorities. Randomisation codes will not be broken for the planned analyses of data until all decisions on the evaluability of the data from each individual participant have been made and documented.

The RTSM will be programmed with blind-breaking instructions. In case of an emergency, in which the knowledge of the specific blinded study treatment will affect the immediate management of the participant's condition (eg, antidote available), the Investigator has the sole responsibility for determining if unblinding of a participants' intervention assignment is warranted. Participant safety must always be the first consideration in making such a determination. If a participant's intervention assignment is unblinded, the sponsor must be notified within 24 hours after breaking the blind. The Investigator documents and reports the action to AstraZeneca, without revealing the treatment given to participant to the AstraZeneca staff.

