
 
To collect and store blood (plasma) and urine samples for potential future exploratory research aimed at exploring biomarkers involved in PK, PD, safety (including anti-platelet antibodies) and tolerability related to AZD8233 treatment or cardiometabolic diseases
 
	
 
Results of potential future exploratory biomarker research may be reported outside this study's CSR
 

 
Optional: To collect and store DNA from blood samples according to each country's local and ethical procedures for future exploratory research into genes/genetic variation that may influence response to treatment.
 
	
 
Results of possible future genetic research may be reported outside this study's CSR.
 

Two analyses are planned for this study:

- A primary analysis after the treatment period,
- A complete analysis after the final follow-up (after final database lock).

[figure not shown]
The two analyses will have the same scope, except for lipoprotein profile which will be included only in the complete analysis, as described in sections 2, 3 and 4. With the aim to maintain the blinding the primary analysis will be performed by an independent unblinded team. The purpose of the primary analysis is to help inform further clinical development; no changes will be made to this study unless a safety signal is observed. This analysis will not have any impact on the overall type-1 error because no changes will be made to the trial based on the outcome of the analysis (all efficacy data is already collected at the point of the primary analysis, no changes to the efficacy model will be made). The primary analysis will be done when all patients still in study have completed the treatment period (visit 10). Additional details will be given in the primary analysis charter and the Unblinded Review Committee (URC) charters (i.e. data cut-off rules, data cleaning, nomination of the unblinded biometrics team and the URC and the operational procedures used to protect the blinding).

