### 1.3 Number of subjects

Approximately 108 participants will be randomly assigned to study intervention such that at least 80 evaluable participants complete the study. Any participant who receives at least one dose of study intervention is considered evaluable and is included in the full analysis set. Participants are randomly assigned to study treatment in a ratio of 1:1:1:1.

The sample size of 20 participants per arm will provide 90% power in a two-sided t-test at 5% significance level to detect a difference of 0.33 on the logarithmic scale; 0.33 on the logarithmic scale is considered sufficient to distinguish the effect of the CCI dose from the effect of the CCI dose. The common SD for log-transformed LDL-C is assumed to be 0.3.

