## **4 ANALYSIS METHODS**

All analyses method described in this section will be applicable to both the analyses, primary and final.

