#### **4.1.3 Sensitivity analysis 1**

The sensitivity analysis 1 will consist of repeating the MMRM assuming a log-normal distribution including only subjects who have completed the treatment period as per protocol and who have no relevant IPDs. Subjects who have completed the treatment period as per protocol are the subjects who reached week 12 and received all four scheduled doses of IP; subjects who received wrong dose of IP or wrong treatment will be excluded. Further, relevant IPDs are defined in section 2.2.

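### Sensitivity analysis 1 tests Week 12 LDL-C but excludes participants for excluded-medication deviations at any time to Week 24, so its two planned runs can use different sets

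*SAP*

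**What the plan says.** SAP 4.1.3 defines sensitivity analysis 1 as a repeat of the log-scale mixed model "including only subjects who have completed the treatment period as per protocol and who have no relevant IPDs". Completion is tied to a time point: the participant must have reached Week 12 and received all four doses. The deviations are not; SAP 4.1.3 refers back to SAP 2.2 for them. SAP 2.2 names five groups: entry criteria (categories 1 and 2), treatment continued after a discontinuation criterion was met (3), investigational product deviations with one exception (5), and "All IPDs included in the category 6 - Excluded Medications taken".

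The visit tested is Week 12, using that visit and earlier scheduled visits (SAP 4.1.1). Protocol 6.5 bars the excluded therapies throughout participation, and restricts new drugs and dose changes until the follow-up visits are complete. The final visit is Day 169 (Protocol 8).

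SAP 1.1 plans a primary analysis, run by an independent unblinded team once all participants still in the study have completed Visit 10, and a complete analysis after final database lock. SAP 4 states: "All analyses method described in this section will be applicable to both the analyses, primary and final".

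**The concern.** An analysis restricted to participants who followed the protocol is meant to show whether the Week 12 result depends on people whose conduct could have disturbed it. Conduct after the Week 12 sample cannot have done so. Excluding for it discards valid Week 12 data and makes membership of the set depend on what happened after the outcome was measured.

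It also makes the set unstable. A participant can be in sensitivity analysis 1 at the primary analysis and out of it at the complete analysis with an unchanged Week 12 value. Two reports would then give different estimates under one name, and a reader could not tell from the SAP which one stands.

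**Working it through.** **1. Which listed categories can newly arise after Week 12?**
- Categories 1 and 2 concern entry, so they are fixed by randomisation.
- Categories 3 and 5 concern study treatment. Doses are on Days 1, 8, 29 and 57, so no new event is expected after Day 85.
- Category 6 concerns medication restrictions that run to Day 169. It is the one that stays open.

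The open window is 169 − 85 = 84 days, out of 169 − 1 = 168 days on study: 84/168 = 50%.

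**2. Does the SAP limit onset elsewhere?** No. SAP 4.2.2 tabulates IPDs both before and on treatment, and SAP Table 5 runs the on-treatment phase to the end of the study. Nothing in SAP 1.1, 2.2, 4 or 4.1.3 freezes the exclusions at the first run.

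**3. How many participants?** The documents give no rate, so these rates are assumptions. Base: 80, the plan's minimum number of evaluable participants (SAP 1.3). With rate r of a first category 6 deviation after the Week 12 sample, the expected number is 80r and the chance of at least one is 1 − (1 − r)^80.

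| r (assumed) | Expected number | Chance of at least one |
|---|---|---|
| 1% | 0.8 | 55% |
| 2% | 1.6 | 80% |
| 5% | 4.0 | 98% |

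As a change between the two runs these are upper figures: participants recruited early may have finished follow-up before the primary analysis.

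**4. The plan's own figure.** SAP 1.3 says: "The sample size of 20 participants per arm will provide 90% power in a two-sided t-test at 5% significance level". The target difference there is 0.33 log units and the assumed SD is 0.3. For n = 20 the standard error (SE) of a pairwise difference is 0.3 × √(2/20) = 0.0949, the noncentrality is 0.33/0.0949 = 3.48 on 38 degrees of freedom, and the exact t-test power is 92.4%. The stated 90% is reached at 19 per arm (91.0%), so the plan's figure is reproduced and slightly conservative.

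**5. How far could the estimate move?** Suppose k participants per arm leave at random between runs, from 20 per arm. The SD of the shift in a pairwise difference is 0.3 × √2 × √(1/(20 − k) − 1/20). The 95% range of the shift in the ratio is exp(±1.96 × SD). This is a simple two-group approximation that ignores the baseline covariate and earlier visits.

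| k per arm | SE after loss | SD of shift (log) | 95% range of ratio shift | Power for 0.33 |
|---|---|---|---|---|
| 1 | 0.0973 | 0.022 | about ±4% | 91.0% |
| 2 | 0.1000 | 0.032 | about ±6% | 89.4% |
| 3 | 0.1029 | 0.040 | about ±8% | 87.5% |

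Four late deviations among 80 is one per arm (4/4 = 1), so the highest rate in step 3 corresponds to the first row.

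**The case against.** **Other documents may settle it.** SAP 2.2 sends the reader to the Non-compliance Handling Plan for deviation details, SAP 3.5 places the detailed list of restricted medications in the integrated data review plan, and SAP 1.1 leaves cut-off and cleaning rules to charters. A cut-off could sit in any of these. This lowers confidence but does not close the gap: SAP 2.2 itself states the exclusion rule for this analysis, without a date, and points to none.

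**A breach of the unblinding rule.** A reader might infer one from Protocol 6.3: "Randomisation codes will not be broken for the planned analyses of data until all decisions on the evaluability" of each participant's data are made and documented. Yet Protocol 9.2 and SAP 1.3 define an evaluable participant as one who received at least one dose, and on that definition evaluability is settled long before Visit 10. A wider reading is arguable, but the documents do not require it.

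**Unblinded results shaping the later set.** Only an independent team is unblinded. SAP 3.5 has the study physician confirm prohibited medications, and nothing shows that those who judge deviations will see results by arm.

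**Bias by arm.** It is tempting to suppose that lipid-lowering drugs are added more often where LDL-C stays high or has risen again, so that exclusions differ between arms. But Protocol 6.5 lets the investigator prescribe necessary treatment outside the excluded list, so an added drug is not always a category 6 deviation. The documents give no evidence of a difference between arms.

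**Small consequences.** This stands. The SAP defines no separate per-protocol population. The primary estimate uses the full analysis set and does not apply these exclusions. Losing one per arm leaves power above 90%, in an analysis that was not itself powered.

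**Conclusion.** The point holds in a limited form. As written, SAP 2.2 and 4.1.3 remove participants from a Week 12 analysis for medication use that began after the Week 12 sample, and SAP 4 lets the set differ between the two reports. That follows from the text and needs no assumption about rates.

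The size does need assumptions and is probably small: about 1 to 4 of 80 participants at late-deviation rates of 1% to 5%. At the top of that range, spread evenly and at random over arms, a pairwise ratio would typically shift by no more than about 4% in either direction. The issue is which participants are counted and whether the result is reproducible. It does not touch the primary conclusion. Severity is minor and confidence moderate, because the handling plan and charters are not available.

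**What to change.** In SAP 2.2 and 4.1.3, limit relevant category 6 deviations to those with onset on or before the participant's Week 12 LDL-C sample. Have blinded staff finalise the exclusion list for sensitivity analysis 1 before the Visit 10 primary analysis, and state that the same list is used in the complete analysis. If the Non-compliance Handling Plan or a charter already does this, a cross-reference is enough.

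Later category 6 deviations would still be tabulated and listed under SAP 4.2.2, so no information is lost. The cost is a short SAP edit and one blinded deviation review before the Visit 10 data cut. No medication restriction changes.

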## 3 BASELINE, EFFICACY AND SAFETY EVALUATION

### 3.1 General principles

#### 3.1.1 Handling of missing data

Missing data are not replaced unless otherwise specified for the statistical models. Only date of first and last dose of IP, AE start and end date and concomitant medications end date are imputed. Imputation rules are reported below.

##### 3.1.1.1 Imputation of date of first dose of IP

Date and time of first dose of IP are mandatory eCRF fields recorded in the treatment log. No Imputations are expected. In the rare cases of missing date, the date of first dose of IP will be imputed if all the following criteria are met:

- There is at least one injection (including lot number) recorded in the eCRF treatment log
- The first recorded injection has a missing or partial missing date

If that is the case, the date of first dose of IP is imputed with the date of eCRF visit Day 1. Completely missing time and time where only hour is missing is imputed to 00:00. If only minutes are missing, then it will be imputed to HH:00.

### 3.1.1.2 Imputation of date of last dose of IP

Date and time of last dose of IP are mandatory eCRF fields recorded in the treatment log. No imputations are expected. In the rare cases of missing date, the date of last dose of IP is imputed if all the following criteria are met:

- There is at least one injection (including lot number) recorded in the eCRF treatment log
- The last recorded dose has a missing or partial missing date

If that is the case, the date of last dose of IP is imputed with the date in which the subject ended the treatment phase recorded in the end of treatment eCRF.

### 3.1.1.3 Imputation of AE end date

Completely missing AE end dates are not imputed. Partial missing AE end dates are imputed as below:

- If the AE is ongoing, the end date is stated to missing.
- If the AE is not ongoing, and if only the day is missing: Assume the last day of the collected month.
- If the AE is not ongoing, and both, the day and the month are missing: Assume 31-DEC of the collected year.

After applying these rules, if the imputed AE end date is after the end of study date or the date of death, the AE end date is set to the earliest date between the end of study date and the date of death.

### 3.1.1.4 Imputation of AE start date

Before to proceed with the AE start date imputation, the first dose of IP and the AE end date are imputed as described in the previous section.

Only partial AE start dates are imputed; Dates which are completely missing are not imputed. Partial dates are imputed as described below:

If the day is missing and the month and/or the year is different from the month and year of the first dose of IP, assume 01-*MMM*-*YYYY*. If the month and year are the same as the first dose of IP month and year and the end date is on or after (including ongoing / missing) the first dose of IP, then assume the date of the first dose of IP. If the month and year are the same as the first dose of IP month and year and the end date is prior to the first dose of IP, then assume the end date.

If the month is missing and the year is different from the year of first dose of IP, assume 01-JAN-*YYYY* of the collected year. If the year is the same as the first dose of IP year and the end date is on or after (including ongoing / missing) the first dose of IP, then assume the date of the first dose of IP. If the year is the same as the first dose of IP and the end date is prior to the first dose of IP, then assume the end date.

After applying these rules, if the imputed AE start date is after a complete AE end date then assume the same date as the complete AE end date; if the end date is missing and the imputed AE start date is after the end of study date then assume the same date as the study end date.

### 3.1.1.5 Imputation of concomitant medications and concomitant procedures end date

Completely missing end dates or dates for which the year is missing are not imputed. Partial missing concomitant medication end dates are imputed as below:

- If the concomitant medication is ongoing, the end date is set to missing.
- If the concomitant medication / procedure is not ongoing, and if only the day is missing: Assume the last day of the collected month.
- If the concomitant medication / procedure is not ongoing, and both, the day and the month are missing: Assume 31-DEC of the collected year.

After applying these rules, if the imputed date is after the end of study date or the date of death, the concomitant medication / procedure end date is set to the earliest date between the end of study date and the date of death.

### 3.1.1.6 Imputation of concomitant medication and concomitant procedures start date

Both, completely missing and partially missing start dates are not imputed.

## 3.1.2 Analysis visit windows

For the purpose of the statistical analysis all parameters, except the adverse event, concomitant medication / procedure, medical history, protocol deviations and other non-compliances reported in the CTMS and some demographic data (sex, ethnic group and race) are allocated to the analysis visit as reported in the tables below. The allocation to visit windows is performed after the imputation of date of first and last doses of IP as in section 3.1.1. Measurements with missing or partially missing dates cannot be imputed to any analysis visit.

**Table 3 Analysis visit windows**

Analysis visit (AVISIT)	Scheduled visit day	Visit Window (Days)	Days of flexibility used to build the visit window
Baseline	D-42 to D1	<=1 a	
Day 1	1	1 b	
Week 1	8	6 – 10	2
Week 3	22	19 – 25	3
Week 4	29	26 – 32	3
Week 6	43	39 – 47	4
Week 8	57	53 – 61	4
Week 10	71	67 – 75	4
Week 12	85	80 – 87	5 - 2

**Table 3 Analysis visit windows**

Analysis visit (AVISIT)	Scheduled visit day	Visit Window (Days)	Days of flexibility used to build the visit window
Week 14	99	92 – 106	7
Week 16	113	107 – 120	7
Week 18	127	121 – 134	7
Week 20	141	135 – 148	7
Week 22	155	149 – 162	7
Week 24	169	163 – 176	7

a Includes all measurements collected before or on day 1 prior to first dose of IP. If the measurement is collected on day 1 but it cannot be determined if it was done before or after the first dose of IP (due to missing time and/or planned time point), then it will be considered as collected after the first dose of IP. For height, weight, BMI and Age if the measurement is collected/derived on day 1, it is always considered as collected before the first dose of IP.

b Includes all measurements collected at day 1 on or after the first dose of IP.

After having assigned the visit windows as described above, if there are measurements which have not yet the analysis visit assigned, they are labelled as reported in the table below.

**Table 4 Analysis visit windows for unscheduled visits**

Analysis visit (AVISIT)	Visit Window (Days)
UNS 1	2 – 5
UNS 2	11 – 18
UNS 3	NA
UNS 4	33 – 38
UNS 5	48 – 52
UNS 6	62 – 66
UNS 7	76 – 79
UNS 8	88 – 91
UNS 9	>=177

The unscheduled visits will be numbered sequentially with an increment of 0.1. For example, if two measurements are done in the unscheduled visits that occur between visit Day 29 and Day 43, then these unscheduled visits will be numbered UNS 4.1 and UNS 4.2 in the order they occurred. The unscheduled visits are not summarized in tables but only presented in listing.

For the purpose of the statistical analysis:

- the baseline value used for statistical analyses is the last available value among those in the baseline analysis visit window. If several measurements are collected during the selected day, the average (for numeric values)/worst (for categorical values) of the measurements is taken. If there are several categorical values corresponding to the worst case, then the last measurement registered in eCRF will be taken.
- all the other post baseline visit values: If more than one measurement falls in the same visit window but in different days, the nearest to the scheduled visit day is taken. If several measurements are collected within the same distance from the scheduled study day, the data of the earlier visit after the scheduled study day within that window is used. If several measurements are collected during the selected day (selected timepoint within the day for PK), the average (for numeric values)/worst (for categorical values) of the measurements is taken. If there are several categorical values corresponding to the worst case, then the last measurement registered in eCRF will be taken. For coagulation parameters and complement activation panel if the selected day is a dosing day (except Day 1), two timepoints within the day need to be considered (pre-dose and 2h post-dose).

Averages are calculated after LLOQ replacement as reported in the following sections.

